Mediational modeling will examine the degree to which putative mechanisms of behavioral change transmit the effects of the intervention on the specified outcomes. BSEM will investigate mediation of treatment effects by hypothesized mechanisms (positive and negative affect and cognitive deficits) utilizing MPlus v. 8.0.¹⁴⁴⁻¹⁴⁶ Measurement of positive and negative affect will use the PANAS. Measurement of cognitive deficits will use the CF-A. Models will evaluate whether change over time (captured using growth factors) in positive affect, negative affect and cognitive deficits, measured with the PANAS and CF-A, mediates the effect of treatment at six months post-partum. Examination of the posterior distribution of the indirect effects will evaluate the probability that mediational effects exist. For model simplicity it may be necessary to break these analyses into two distinct mediation models. However MCMC estimation has demonstrated superior small sample performance relative to maximum likelihood-based approaches in continuous, normally distributed data.^{147, 148} As discussed in the **Specific Data Analytic** section, minimal variability in growth factors representing change over

time, which may be partially a function of small sample size will result in use of an alternative approach.

Specific Data Analyses: Aim 4

The specific quantitative, analytic plan will focus on Primary Aim 4 and Secondary Aim 1.

Primary Aims

Aim 4 (Stage IB)

Conduct a preliminary randomized trial with depressed pregnant smokers comparing the BA to HW to evaluate the following: 1) The effect of BA on abstinence at 4 ½ months postpartum, which is a primary outcome. Logistic modeling will evaluate smoking abstinence, measured by biochemically verified TLFB, at 4 ½ months postpartum as a function of treatment group. **2) The effect of BA on depression at 4 ½ months postpartum, which is a primary outcome.** Generalized linear modeling will evaluate depression, measured by the PHQ-9, at 4 ½ months postpartum as a function of treatment group. **3) Feasibility of depressed pregnant smokers' acceptance of the smartphone delivery of BA and HW, and assessment components indicated by a) retention, which is a primary outcome, b) completion of prenatal and postpartum sessions, which is a primary outcome c) completion of study assessments, which is a secondary outcome d) strength of therapeutic alliance from both the participant and therapist perspective, which is a secondary outcome and e) participant and therapist ratings on satisfaction questionnaire, which is a secondary outcome.** Survival analysis will evaluate retention by modeling time to drop-out as a function of treatment condition. Binomial logistic modeling will evaluate the proportion of completed sessions as a function of treatment condition across the entire study as well as in the pre-natal and post-partum periods separately. Generalized linear models will evaluate participant and clinician measures of therapeutic alliance, measured by the WAI, as a function of treatment group. Similarly, generalized linear modeling will evaluate satisfaction as a function of treatment group. **4) Feasibility of study procedures as indicated by a) percentage of sessions interrupted by technical difficulties, which is a secondary outcome, and b) percentage of urine tests (cotinine and/or anabasine) received for biochemical verification of self-reported abstinence at 4 ½ months postpartum follow-up, which is a secondary outcome.** Binomial logistic models will evaluate the proportion of sessions interrupted for technical difficulties and the proportion of biochemically verified abstinence measures as a function of treatment. These analyses will provide estimates with 95% credible intervals for each of these proportions in each group that will permit assessment of feasibility.

Specific Analyses: Secondary Aim 1 (Stage IB)

Evaluate change in hypothesized treatment mechanisms including positive affect, negative affect and cognitive impairment in relation to treatment effects on smoking and depression. It would be ideal to evaluate the change in positive affect, negative affect and cognitive impairment as mediators of treatment effects on 4 ½ month post-partum outcomes via structural equation modeling. Specifically, we could model the change over time in each mediator and evaluate the degree to which each growth factor might transmit the effect of treatment. However, it is possible that a sample size of N = 50 will not provide enough variability to estimate certain parameters implied by such a model (e.g. the slope of change in each of these mediators may have minimal variance and function poorly as a mediator). If this latter scenario obtains, we will evaluate each component of a mediational analysis in separate analyses to evaluate the evidence for mediation of treatment effects by positive affect, negative affect and cognitive impairment. Specifically we will: a) evaluate the change over time in each mediator as a function of treatment using multi-level modeling; b) Evaluate the effect of

treatment on the outcome (smoking cessation or depression); and c) evaluate the outcome (smoking cessation or depression) as a function of change in the mediator captured either through a difference score (six months – baseline) or residual change score (six months residualized on baseline). While the former (SEM) approach would provide a more elegant test of the overall model of behavior change, the latter may be necessary based on the properties of the sample.

PARTICIPANT SAFETY MONITORING PLAN

Assessment of Worsening Depression, Anxiety and Suicide Risk

As outlined in the Safety Monitoring Protocol and Procedures (see Appendix), we will evaluating and assessing the severity of depressive and anxiety symptoms, other psychiatric disorders as well as suicide risk, using information from the PHQ-9, C-SSRS, and MINI administered at screening (AIM 1), and the PHQ-9, C-SSRS, MINI and Generalized Anxiety Disorder – 7 (GAD-7), administered at screening (AIM 3 & Aim 4). Additionally, we will be assessing for depressive and anxiety symptoms and suicide risk at the counseling sessions throughout treatment and have outlined procedures for monitoring changes of these symptoms and ideations (Appendix Safety Monitoring Plan). The document also outlines procedures for addressing other mental health concerns, reporting of elder or child abuse and neglect, domestic/intimate partner violence and crises that occur during sessions.

Participants who are rated on the Columbia-Suicide Severity Rating Scale at screening as having active suicidal ideation with some intent to act and active suicidal ideation with specific plan and intent, who fall within the extremely severe range of depressive symptom severity, who endorse having severe vegetative symptoms, bipolar symptoms, psychotic symptoms, or who are experiencing symptoms associated with Axis I disorders that place them at risk of harm will be further evaluated by a designated Master's or Ph.D. level Mental Health Professional (MHP) to make an appropriate treatment disposition. When needed, participants will be referred to collaborators at The University of Texas Health Science Center (UTH) to manage the action plan/treatment interventions as they deem appropriate or provided with outside referral(s).

Vulnerable Subjects

There is no additional risk to pregnant women and their fetuses posed by participation in the study. The intervention seeks to reduce smoking and depression in women in both the prenatal and postpartum period. Reduction in smoking and depression during these periods may benefit both the woman, the fetus and the neonate.

Procedures to protect confidentiality include: 1) Study participation will be confidential and not included in participants' medical records. 2) Confidentiality will be protected by identifying all subjects by ID numbers only with their names kept within a MD Anderson approved secure web-based applications and institutionally approved databases (see Data management, Quality, and Security section). 3) Participants will not be identified in any public reports or documents. Only the PI and data manager have access to the master file linking ID and other data to participant names. All information will be reported in aggregate form and individual participants will not be identified in any public reports or documents. We expect these procedures to be highly effective for protecting participant confidentiality.

Information collected during participation in the study will be kept confidential. In order to protect the participant's information, we received a NIDA (National Institute on Drug Abuse) Certificate of Confidentiality. We will treat all responses confidential to the extent possible. We will follow the HIPAA rules as mandated by MD Anderson and NIDA.

DATA MANAGEMENT, QUALITY & SECURITY

As part of the ongoing monitoring of the project, study investigators and staff are responsible for ensuring that data quality assurance procedures are developed and maintained. Several procedures will be used to maintain the integrity of the data.

REDCap For AIM 1, process measures, participant contact and clinical progress notes will be collected and managed using REDCap (Research Electronic Data Capture, www.project-redcap.org) electronic data capture tools hosted at MD Anderson. REDCap is a secure, web-based application with controlled access designed to support data capture for research studies, providing: 1) an intuitive interface for validated data entry; 2) audit trails for tracking data manipulation and export procedures; 3) automated export procedures for seamless downloads to common statistical packages; and 4) procedures for importing data from external sources. In the case of multi-center studies REDCap uses Data Access Groups (DAGs) to ensure that personnel at each institution are blinded to the data from other institutions. REDCap (<https://redcap.mdanderson.org>) is hosted on a secure server by MD Anderson Cancer Center's Department of Research Information Systems & Technology Services. REDCap has undergone a Governance Risk & Compliance Assessment (August 2016) by MD Anderson's Information Security Office and found to be compliant with HIPAA, Texas Administrative Codes 202-203, University of Texas Policy 165, federal regulations outlined in 21CFR Part 11, and UTMDACC Institutional Policy #ADM0335.

Trained data collectors will use the databases uploaded to or enter directly into the MD Anderson REDCap system. Automated prompts may facilitate some participant contact and treatment delivery activities. MD Anderson's Research Information Systems and Technology Services (RISTS) group provides deployment and integration support for research data management using the REDCap (Research Electronic Data Capture; www.project-redcap.org) application.¹⁴⁹ REDCap (<https://redcap.mdanderson.org>) allows researchers and program directors at MD Anderson to create projects with data collection instruments and share those projects with colleagues. Researchers and program directors can capture and analyze data through a simple web-based interface. REDCap is a two-tier pHP-based web application that can be hosted on a variety of hardware and operation systems.

For AIMs 3 & 4, all data will be stored in the institutionally approved Tobacco Research and Treatment Program (TRTP) database (APPID-264846) in a centralized location on institutional servers behind the firewall, which is backed up daily, with access limited to specific users at the discretion of the PI. The PI will assure that audits of selected subsets of data are performed and that appropriate safeguards of participant privacy are maintained. Privacy safeguards will include appropriate password protection and physical security for all computer systems.

Additional quality assurance procedures include a data collection protocol documented in a procedure manual; and regular meetings between the study statistician, the PI, data managers, and other project staff to review problems and solutions, and discuss concerns. Data entry systems, whether via Qualtrics or hand entry with verification, specifically provide field checks, range checks for continuous variables and valid value checks for categorical variables; checks for legitimate dates and times and logical consistency. During data collection, we will

issue reports weekly, or even following any new data entry, depending on the needs of the project. Queries and reports will be provided to the PI. Preliminary review will be initiated shortly after data collection begins to allow monitoring of data quality.

Videoconferencing Software We will work with MD Anderson Infosecurity to identify a HIPAA compliant videoconferencing software package through which to deliver the treatment sessions.

Focus Group Protected Health Information Data and identifiers from focus group audiotaped interviews will be stored behind the institutional firewall on encrypted servers with restricted access only to study team members and will not be reused or disclosed to any other person or entity (except where required by law), or for other research, without prior approval from the IRB. Electronic data and identifiers will be retained indefinitely on MD Anderson servers behind the institutional firewall and will be archived per institutional standards.

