- 4) Self report smoking, even a puff, cigarettes, little cigars and/or cigarillos in the past 30 days.
- 5) Gestational age between 18 to 32 weeks
- 6) Able to speak and follow verbal and written instructions in English
- 7) Subjects must report a current residence in the State of Texas and must not have plans to move out of the state in the next 7-8 months
- 8) Subjects will confirm positive pregnancy status through study provided pregnancy test or provide paperwork verifying pregnancy status if the pregnancy test is inconclusive
- 9) Willing to refrain from the use of other nicotine/tobacco products for the duration of the study
- 10) Agree to be treated via telehealth (live audio-video conference and phone) and to be contacted via text and/or email
- 11) Provide informed consent and agree to all assessments and study procedures
- 12) Interested in treatment that might change smoking behavior or help them quit smoking
- 13) Be the only participant in their household currently receiving treatment on this protocol

Exclusion criteria for Aim 4

- 1) Currently participating in individual psychotherapy
- 2) Currently participating in other smoking cessation treatments and refuses to refrain from use for the duration of the study
- 3) Rated on the Columbia-Suicide Severity Rating Scale¹¹³ at screening as in the past month having had active suicidal ideation with some intent to act or active suicidal ideation with specific plan and intent (indicated by answering "YES" on both Q3 and Q4, and/or 5) and/or endorsing "YES" to having engaged in preparatory acts towards or attempting suicide in the past 3 months (as indicated by answering "YES" to both parts of Q6)
- 4) Have a lifetime or current diagnosis of Psychotic Disorder as assessed by specified Mini International Neuropsychiatric Interview (MINI) 7.0.2 modules.

- 5) Have a past or current diagnosis of Bipolar Disorder I or II or have a past or current diagnosis of Other specified Bipolar and related disorder as assessed by specified MINI 7.0.2 modules.
- 6) Any otherwise not specified medical or psychiatric condition, illness, disorder, or concomitant medication that could compromise participant safety or treatment, as determined by the Principal Investigator and/or Study Physician.
- 7) Participant considered by the investigator as unsuitable candidate for full participation in the study.

Inclusion criterion for Secondary Aim 2, Stage IB

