Acceptability of treatment -			x	x	x	x	x	x	x	x	x	x	x	
Acceptability of treatment - Clinician														

(a). MINI Modules: (A, C, D, E, F, G, H, K, N, O)

(b). C-SSRS may be done at any visits as clinically indicated by the Safety Plan

(c). Urine test (cotinine and/or anabasine) will be done at visits where the participant is reporting abstinence and meeting the 7 day point prevalence criteria.

(d). Urine pregnancy test, or if preg test result inconclusive submit paperwork verifying pregnancy

(e). Follow up on any open CCMs/Psychotherapy/Treatments & AEs ONLY

(f). Administer Participant Acceptability of treatment if ppt did not complete at previous timepoints

(g). Clinician Acceptability of treatment may be completed earlier if ppt withdraws from the study

AIM 4: Table 2. Postpartum

Timeline	1 month break after birth of baby	Postpartum Visits (PP)				FU visit
Beginning of Treatment Week		4 visits over 6 weeks				4.5 months from PP
	BIRTH	PP1	PP2	PP3	PP4	FU
Table 2. Screening Assessment Schedule						
Telephone script & screen (basic eligibility)						
Informed Consent verbal/signed						
MINI (a)						
Childhood Trauma Questionnaire						
C-SSRS (b)						
TLFB		x	x	x	x	x
FTND						
Smoking History Form						
Medical History						
Urine Test (urine cotinine and/or anabasine collection) - (c)		x	x	x	x	x
Urine pregnancy test (d)						
Concomitant Medications, Other smoking cessation medications_ treatments & other Psychotherapy		x	x	x	x	x (e)
OUTCOME MEASURES						
PHQ-9		x	x	x	x	x
GAD-7		x	x	x	x	x
NICOTINE WITHDRAWAL						
WSWS-28		x	x	x	x	x
MEDIATORS						
PANAS		x	x	x	x	x
PROMIS Cognitive function-abilities		x	x	x	x	x
OTHER						
Counseling		x	x	x	x	
Adverse Events		x	x	x	x	x (e)
Assessment of Changes since last visit		x	x	x	x	x
FEASIBILITY MEASURES						
WAI-Client Short		x		x		
WAI - Therapist		x		x		
Technical issues questionnaire		x	x	x	x	
Acceptability of treatment -		x	x	x	x	x (f)
Acceptability of treatment - Clinician					x (g)	

(a). MINI Modules: (A, C, D, E, F, G, H, K, N, O)

(b). C-SSRS may be done at any visits as clinically indicated by the Safety Plan

(c). Urine test (cotinine and/or anabasine) will be done at visits where the participant is reporting abstinence and meeting the 7 day point prevalence criteria.

(d). Urine pregnancy test, or if preg test result inconclusive submit paperwork verifying pregnancy

(e). Follow up on any open CCMs/Psychotherapy/Treatments & AEs ONLY

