Timeline Follow-back Interview (TFBI)¹¹¹ Self-reports of smoking will be collected from participants in Aims 3 and 4 at baseline using the TFBI. Starting at study entry, self-reported smoking will be collected daily with the daily diary Ecological momentary assessments (EMA) through the Qualtrics platform. In the event the participant does not complete the EMA daily diary, smoking data will be collected at counseling visits.

Biochemical Abstinence Verification All participants who self-report as being abstinent at each treatment visit will be sent a urine test (cotinine or anabasine)to biochemically verify abstinence. Participants will be asked to send a picture of the urine test to the research staff via text message or email and/or return the urine samples via mail in the labeled box provided to them. This process is used in several of our smoking cessation studies and offers the patient a convenient way to verify smoking and to also provide remote biochemical verification of self-reported abstinence. We will use a urine cotinine test that measures nicotine at 100 ng/mL, with a negative result to verify abstinence. Abstinence Definitions Point-prevalence abstinence at the end of prenatal treatment and end of postpartum treatment and 4 ½ months postpartum follow-ups will be defined as both a self-report of not smoking during the previous 7 days and a negative result. Regarding the primary outcome of abstinence at 4.5 months postpartum, because the study will allow for a variable quit date through the postpartum period, we will consider quit attempts up to week 14 of the postpartum period, which will allow for the recommended 2-week grace period for prolonged abstinence prior to the postpartum end of treatment. Thus, prolonged abstinence at 4.5months postpartum will be defined as a self-report of not smoking from Week 16 through the 4.5-months postpartum follow-up and a negative result .

The PHQ-9¹¹⁹ will be used to assess depression outcomes. The PHQ-9 has been found to reliably measure response to depression treatment, including responsiveness to criterion standards for full, partial and remission of DSM-IV symptoms of major depression.¹²⁰

The GAD-7 will be used to asses anxiety outcomes. The GAD-7 is a validated, seven-item scale developed to assess the presence and severity of generalized anxiety disorder symptoms over the last two weeks. Empirically-derived cut-offs can be used to quantify severity of reported symptoms.

Treatment Mechanisms

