the estimated frequencies, coupled with the low numbers in the control condition we chose to round any fraction for abstinence upward. This had the effect of producing a slightly higher effect in the control condition (n = 3 versus n = 2 abstinent) therefore rendering the simulated effect size more conservative). A fundamental difficulty is that the Frequentist approach cannot provide any indication regarding the relative probability of different values within the 95% Confidence Interval being the true parameter. The Bayesian estimate of the relative risk is slightly different (rounding was necessary in estimating the Frequentist but not the Bayesian solution), RR = 2.73, (95% CI: 0.90-11.44), however since these estimates are based on a posterior distribution it is possible to discuss the probability that an effect of a given magnitude is the governing parameter. Defining benefit as any RR > 1, the simulated posterior distribution shows that there is a 96% chance that the intervention confers this benefit and a more stringent definition (Relative Risk ≥ 1.50) is associated with an 85% probability that intervention confers

benefit. We stipulate that an intervention effect that has at least a 75% probability of increasing the relative risk of abstinence by >1.25 will warrant further investigation in a larger trial. While the above simulation provides a straight-forward example of how Bayesian modeling works, it is often necessary to use more sophisticated Bayesian approaches (e.g., logistic regression with Monte Carlo Markov Chain estimation methods). As such, final analyses will utilize Bayesian generalized linear modeling with multilevel-modeling for repeated measures data.

Bayesian Modeling Strategy Initial analyses examining group differences for baseline variables will use cross-tabulation, ANOVA's, and examination of correlations between baseline variables and specified outcomes. For the purposes of evaluating the comparability of groups, a posterior probability of $\geq 95\%$ will constitute evidence for statistically reliable differences. Baseline or demographic variables on which group differences are detected, and which are correlated with outcomes, meet the definition of confounders^{136, 137} and will result in two sets of analyses: one in which the relevant variable is included as a covariate and one in which it is not. This will permit determination of the degree to which any group differences might confound conclusions regarding treatment.

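### Women already smoke-free for 7 days can be randomised, and the primary abstinence analysis does not separate them from women smoking at entry; if BA helps them relatively less, the RR behind the go decision is pulled toward 1

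*Combined protocol and SAP*

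**What the plan says.** **Entry.** Inclusion criterion 4 under Eligibility Criteria: AIM 4 reads "Self report smoking, even a puff, cigarettes, little cigars and/or cigarillos in the past 30 days". No criterion sets a minimum smoking rate, requires smoking in the last week, or asks for a test showing current smoking. Criterion 12 adds only "Interested in treatment that might change smoking behavior or help them quit smoking".

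**Outcome.** Under Outcome (Abstinence Definitions), point-prevalence abstinence, including at 4½ months postpartum, "will be defined as both a self-report of not smoking during the previous 7 days and a negative result". The same paragraph then turns to the primary outcome and says "prolonged abstinence at 4.5months postpartum will be defined as a self-report of not smoking from Week 16 through the 4.5-months postpartum follow-up", again with a negative test.

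**Urine testing.** The footnote to Table 2 states: "Urine test (cotinine and/or anabasine) will be done at visits where the participant is reporting abstinence and meeting the 7 day point prevalence criteria". The section Baseline Screening Phone Visit says that Aim 4 urine kits are mailed in a second package, after randomisation at Visit 1.

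**Allocation and analysis.** Minimisation uses baseline depression, smoking rate and gestational age, with no cut-points given. Specific Data Analyses: Aim 4 models abstinence by logistic regression on treatment group. Under Bayesian Modeling Strategy, a baseline covariate enters a second analysis only if the arms differ on it (posterior probability of at least 95%) and it correlates with outcome. Missing smoking data count as non-abstinent.

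**Decision rule.** Under Simulated Example, an effect with "at least a 75% probability of increasing the relative risk of abstinence by >1.25 will warrant further investigation in a larger trial".

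**The concern.** The 30-day entry window is longer than the 7-day outcome window. A woman who last smoked 8 to 30 days before screening enters as a smoker while already meeting the self-report half of the point-prevalence definition. If she stays quit she is later a success, and under the prolonged definition too, since she is smoke-free from Week 16 onward.

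For such a woman the question is whether BA prevents relapse. For a woman smoking at entry it is whether BA brings about cessation. The primary analysis returns one RR for the mixture. Minimising on smoking rate may balance the two kinds of women across arms, but it leaves them both in the outcome. That balance also makes the covariate rule less likely to be triggered, so a probable strong predictor of outcome would usually stay out of the model.

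Two things are at stake: the chance of passing the go rule when BA works in women who smoke, and the control rate and effect size carried into the next trial.

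**Working it through.** **1. The plan's own example.** With Beta(1,1) priors, 30 per arm and rates of 7.6% and 25%, the posteriors are Beta(3.28, 28.72) and Beta(8.5, 23.5). Two million draws give a median RR of 2.75 (95% interval 0.90 to about 11.5), P(RR>1) = 0.96 and P(RR≥1.5) = 0.85. The plan states 2.73 (0.90–11.44), 96% and 85%, so its method is reproduced.

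**2. Inputs.**
- From the plan: control 7.6%, BA 25%; go if P(RR>1.25) ≥ 0.75; Beta(1,1) priors. The sample size is up to 50 in the Aim 4 design section and 60 in the statistical section, so 25 and 30 per arm are both shown.
- Assumed: the plan's rates apply to women smoking at entry. A share q is already abstinent at randomisation. Of these, a_C (HW) and a_B (BA) are abstinent and verified at 4½ months. The documents give none of q, a_C or a_B.

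**3. Formulas.**
- p_C = (1−q)(0.076) + q·a_C
- p_B = (1−q)(0.25) + q·a_B
- RR = p_B / p_C
- Chance of a go: the sum of binomial probabilities over all pairs of event counts that satisfy the rule.

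**4. One case in full.** Take q = 20% and a_C = a_B = 40%.
- p_C = 0.8 × 0.076 + 0.2 × 0.40 = 0.0608 + 0.0800 = 0.1408
- p_B = 0.8 × 0.25 + 0.2 × 0.40 = 0.2000 + 0.0800 = 0.2800
- RR = 0.2800 / 0.1408 = 1.99, against 0.25 / 0.076 = 3.29 with q = 0

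**5. Range.**

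| q | a_C v a_B | RR | Go, 25 per arm | Go, 30 per arm |
|---|---|---|---|---|
| 0 | – | 3.29 | 72% | 78% |
| 10% | 10% v 10% | 3.00 | 67% | 72% |
| 10% | 30% v 30% | 2.59 | 63% | 69% |
| 20% | 40% v 40% | 1.99 | 52% | 57% |
| 30% | 50% v 50% | 1.60 | 42% | 44% |
| 20% | 40% v 50% | 2.13 | 58% | 63% |
| 20% | 25% v 40% | 2.53 | 65% | 71% |
| 20% | 20% v 40% | 2.78 | 69% | 75% |
| 20% | 20% v 50% | 2.98 | 74% | 80% |

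**6. When dilution occurs.** The pooled RR is an average of the two groups' RRs weighted by control-arm successes, so it falls below 3.29 whenever the RR among already-abstinent women is below 3.29. This is certain once a_C exceeds 1 / 3.29 = 30.4%, because a_B cannot exceed 1. A lower RR need not mean a lower chance of a go: in the last row the extra events more than make up for it.

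**7. No effect in anyone.** The chance of a go stays at about 13% or below. The risk is a missed signal rather than a false one.

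**The case against.** A reader might infer that these women are successes from the day they enter. The documents do not support that. They must stay quit, or quit again, through late pregnancy, birth and 4½ months postpartum, test negative and be retained. The protocol's background reports heavy postpartum relapse: a pooled 94% smoking at 6 months postpartum, and 9% abstinent among the most depressed HW women in the earlier trial.

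A reader might also infer that their successes have nothing to do with treatment, so that dilution is inevitable. That does not follow either. The background calls for support of both abstinent and non-abstinent women, and the postnatal counselling covers cessation or relapse prevention according to smoking status. The endpoint is abstinence rather than new quitting, and measuring it in recently smoking depressed women is a legitimate choice. The large losses in the table come from setting BA's effect on relapse to zero. When BA doubles the share staying quit (20% v 40%), the chance of a go is 69% against 72%.

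Both points limit the size of the concern. They do not answer the remaining part: nothing in the plan identifies these women in the analysis, so a pooled RR near 1 could not be read as failure in cessation, failure in relapse prevention, or a mixture. The review of eligibility at Visit 1 and the interest-in-treatment criterion do not exclude them.

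**Conclusion.** The concern holds in conditional form. Women who already meet the 7-day self-report criterion can be randomised, and the planned primary analysis neither separates nor adjusts for them. If BA's relative benefit is smaller in them than in women smoking at entry, the pooled RR moves toward 1 and the go rule is harder to meet.

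With no BA effect on relapse, 10–30% already abstinent and 30–50% of those staying quit, the RR lies between 2.59 and 1.60 and the chance of a go between 63% and 42% at 25 per arm, against 3.29 and 72% with none. With a substantial relapse-prevention effect the loss is small or absent. These figures rest on assumed shares and relapse rates, and on applying the simulated example's rates to women smoking at entry. They show what could happen and are not a forecast. The documents do not support a claim that the RR will be diluted, nor that these women should be excluded.

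**What to change.** Leave eligibility unchanged.

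1. At Visit 1, before randomisation, classify each woman from Timeline Follow-back self-report as having smoked or not in the previous 7 days. Do not make this depend on urine, because the kits are mailed only after randomisation.
2. Make no smoking in the past 7 days its own level of the existing smoking-rate minimisation factor.
3. Pre-specify this status as a covariate in the abstinence model, whether or not the arms differ at baseline.
4. Report abstinence and the RR by entry status, descriptively, next to the all-randomised result, so that the next trial can be planned for the population it will enrol. The covariate alone does not separate the two groups' RRs; this breakdown does.

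**Cost.** SAP wording, one level in the minimisation program, and making sure the smoking interview comes before allocation at Visit 1. No new measure is needed. The added model term must be estimated from few events: at the plan's rates, 25 × 0.076 + 25 × 0.25 ≈ 8 successes in total. The estimate in women smoking at entry rests on about 18–22 per arm if 10–30% are already abstinent (25 × 0.7 = 17.5; 25 × 0.9 = 22.5), so it should be read as descriptive.
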